10.0 Clinical Laboratory Assessments

10.1 Screening Assessments

A central laboratory will perform clinical laboratory tests conducted at screening to establish medical eligibility. Effective clinical lab normal ranges will be provided by the clinical laboratory and kept on file in the ISF. Abnormal clinically significant clinical laboratory results will be reported as a part of Medical History and must be recorded on the Medical History CRF page. The PI will examine laboratory assessments gathered during screening to assess subject eligibility using the appropriate list of normal ranges to conclude whether subjects are eligible for the protocol, and will indicate justification for admitting subjects with abnormal values, after consultation with the Medical Monitor.

The following laboratory assessments will be performed as a part of screening:

Serum electrolytes and metabolic profile, which includes:

- ALT/SGPT
- Albumin:globulin (A:G) ratio
- Albumin, serum
- Alkaline phosphatase, serum
- AST/SGOT
- Bilirubin, total
- BUN:creatinine ratio
- Calcium, serum
- Carbon dioxide
- Chloride, serum
- Creatinine, serum
- Globulin, total
- Glucose, serum

- Potassium, serum
- Protein, total, serum
- Sodium, serum

CBC, which includes:

- Hematocrit
- Hemoglobin
- MCV
- MCH
- MCHC
- RDW
- Percentage and absolute differential counts
- Red blood cell (RBC) count
- White blood cell (WBC) count

Urinalysis, which includes:

- Color
- Appearance
- Specific gravity
- pH
- Protein
- Glucose
- Ketones
- Occult blood
- Leukocyte esterase
- Nitrite
- Bilirubin
- Urobilinogen

Thyroid function, which includes:

- TSH high sensitivity
- Free T4
- Free T3

HIV serology will be performed.

A **urine-dip pregnancy test** for females of childbearing potential will be performed. The urinary pregnancy tests and drug tests will be performed at the study site.

The central laboratory that will perform screening assessments, other than the urine drug screen and pregnancy tests, is:

LabCorp
[name]
[name]

[contact]
[contact]

10.2 Biomarker Analysis

Biomarker laboratory analyses will be performed using plasma for OT, AVP, and CORT collected from all subjects at the Harbor-UCLA Medical Center according to the Time and Events Table. For blood samples, a butterfly needle will be used to draw 30mL of blood into chilled EDTA vacutainer tubes. Samples will be immediately placed on wet ice. Plasma will be extracted by centrifugation in a refrigerated (4°C) centrifuge at 1,300g for 10 minutes, aliquotted into individual tubes, and stored at -80°C at Harbor-UCLA Medical Center prior to shipment to the collaborating site at Stanford University Medical Center. Biomarker analyses will be performed by [name] and [name] in [name] laboratory at the Stanford University Medical Center in Stanford, California (collaborating site). Concentrations of OT and AVP will be quantified using commercially available enzyme immunoassay kits (Enzo Life Sciences, Farmingdale, New York) and concentrations of CORT will be quantified using radio immunoassay kits (Siemens, Deerfield, Illinois) that have been validated for use in humans. These kits are highly specific and exclusively recognize OT, AVP and CORT respectively, and not related peptides. Plasma samples are extracted using Strata-X columns and then assayed in duplicate and measured using a tunable microplate reader for 96-well format according to manufacturer's instructions.

11.0 Study Monitoring, Auditing, and Documentation

Prior to trial initiation, the CI must provide to MAPS a fully executed and signed FDA Form 1572 and a Financial Disclosure Form. Financial Disclosure Forms also must be completed for all sub-investigators listed on the Form 1572 who will be directly involved in the treatment or evaluation of research subjects in this trial.

The CI, therapists, and study staff will be trained prior to the start of the study. The trial will be administered and monitored by employees or representatives of the sponsor. The site and collaborating sites will be monitored as appropriate for the rate of enrollment in order to comply with GCP guidelines and to ensure validity of the study data. During each monitoring visit, source data verification will be performed to ensure compliance, including accurate and complete recording of data on CRFs, source documents, and drug accountability records. A CRF collation supplied by the sponsor will be completed for each subject enrolled. Study monitor contact information, monitoring and auditing procedures will be supplied in a separate document.

During or after the study, the regulatory authorities, the IRB, and/or representatives of the sponsor may request access to all source documents, CRFs and other protocol documentation for on-site audit or inspection.

12.0 Data Analysis

This study is primarily a safety study that will also obtain estimates of effect size comparing MDMA vs. placebo using observer-blind data from the LSAS as the primary outcome measure. MDMA doses are not expected to differ greatly in treatment outcomes and will be combined for effect size estimates. Descriptive statistics will be computed overall for MDMA and placebo, and within the MDMA dose groups for all available data from outcome measures, including minimum, maximum, average, and standard deviation. Distributional characteristics will be examined for outliers and extreme values and, if either is evident, nonparametric statistics will be utilized in the analysis. Effect size for all outcome measures will be estimated using Cohen's techniques.

The sponsor will examine MDMA and placebo groups for homogeneity through comparing demographic characteristics. There is no expectation that conditions will differ in composition by gender, race or ethnicity, duration of autism diagnosis, or presence versus absence of other permitted psychiatric disorders, such as depression. However, owing to small sample size, such variations may arise by chance. If MDMA and placebo subjects differ upon a demographic variable, then the effects of this variable will be taken into account when looking at safety analyses. No systematic differences are expected.

Primary and secondary outcome measure scores will be plotted across each time of administrations for trend analyses. The number of intervals will vary in accordance with times listed for each measure, but will include in most cases baseline, one or more times after the first experimental session, one or more times after the second experimental session and at six month follow up. Plots will be made for MDMA and placebo subjects, and if trends occur for MDMA subjects, separate exploratory plots will be made for outcome measures after 0, 75, 100 and 125 mg MDMA.

The main estimates of effect size from blinded data will be conducted after the outcome measure assessments at the six-month follow-up are complete for all subjects. Data from all doses of MDMA during Stage 1 (n=16), to be compared with all data from placebo sessions (n=8), with each experimental session treated as an independent observation. The MDMA condition will encompass both Group 1 and Group 2 MDMA doses. Estimates of effect size will be obtained from BDI-II, STAI, PSS, IRI, RSES, ERQ, TAS-20, and QoL-Q scores collected pre-treatment, during and after each experimental session, and the follow-up period, with p value set at 0.05. Effect size will be used to determine the appropriate sample size for future studies.

Scores for BDI-II, STAI, PSS, IRI and RSES completed after each of the experimental session will be averaged to produce mean scores for these periods, including a post-experimental session 1 and post-experimental session 2 average score. BDI-II, STAI and PSS scores gathered via postal mail at monthly intervals from two to five months after the second experimental session will be averaged to produce mean scores for the follow-up period. Missing responses will be replaced with the sample average. These averages will be used for estimates of effect size.

TASIT scores will be compared assessing baseline, after experimental session 1, after experimental session 2, at integrative session six and at 6-month follow up. Correlations between TASIT scores and LSAS scores at the time point following each TASIT score will be made to see whether increased awareness of social cues is associated with reduced social anxiety. MDMA dose will be used as a covariate in order to examine the potential relationship between dose and changes in one or more variable, with dose (75, 100 or 125 mg) serving as the covariate.

Biomarkers will be evaluated for predictive and prognostic power. Separate estimates of effect size will be performed for OT, AVP and CORT. Changes in biomarker concentrations from pre-treatment levels will be used to analyze effects of acute dosing and to determine the time-course of elevated OT and AVP levels post-drug. Pre-treatment biomarker concentrations will be evaluated for predictive power using an exploratory hierarchical regression analysis with condition assignment in Stage 1 and biomarker concentrations at baseline as predictors and treatment outcomes as dependent variables. One regression will be performed with biomarker values taken at the second experimental session. A second regression will be performed on biomarker values taken two weeks after the second experimental session.

TAS-20 scores will be evaluated for predictive power using an exploratory hierarchical regression analysis with condition assignment in Stage 1 and TAS-20 scores at baseline as predictors and with LSAS scores as dependent measures. One regression will examine the predictive power of condition and baseline TAS-20 scores upon LSAS scores one month after the first experimental session and the other will investigate whether condition and baseline TAS-20 and will predict LSAS score at one month after the second experimental session.

Subjects who discontinue treatment prior to the second experimental session will be asked to complete the final outcome assessment prior to continuing to the 6-month follow-up whenever possible. The data from these subjects will be tested for equivalence to data from subjects completing the study per protocol. If found to be equivalent, data from these subjects will be combined for an exploratory intent-to-treat effect size estimate to examine results without bias towards subjects more likely to complete the study per protocol.

Stage 1 and Stage 2 outcomes in extension subjects will be compared after the outcome measure assessments are complete for all extension subjects.

Descriptive statistics will be computed for vital signs and subjective distress during each experimental or open-label session. The sponsor will compare pre-drug and post-drug peak blood pressure, heart rate, and body temperature during and after all experimental sessions by condition and MDMA dose. Analyses will compare peak vital signs between MDMA and placebo subjects, and a separate analysis will consider the effects of dose (0, 75, 100 or 125 mg MDMA) upon vital signs.

Frequency tables will be produced on prevalence of spontaneously reported reactions and AEs. Number and severity of spontaneously reported reactions will be compared in MDMA and placebo subjects using a one-way analysis of variance (ANOVA). The effects of MDMA dose upon number and severity of spontaneously reported reactions will also be assessed. Presence and degree of exacerbated symptoms across MDMA and placebo participant will also be examined.

Perceptions of study participation will be examined at baseline, 6-month follow-up, and end of Stage 2 using the Feedback Questionnaire and a qualitative interview. The results of this qualitative analysis will inform the sponsor of expectancies and perceptions about study procedures for future protocol development. Similarly, belief of condition assignments collected during Stage 1 will be used to assess the effectiveness of the double-blind in preparation for future studies. Results from the Feedback Questionnaire and safety data will be utilized to find the appropriate active MDMA dose for future studies.

To facilitate the planning of future studies, a preliminary estimate of effect size may be performed after all the subjects have completed the outcome assessments, one month after the second experimental session, but not all subjects have completed the six-month follow-up evaluation. This preliminary estimate will consist of safety and outcome measures. Results of the preliminary estimate will have no effect on study conduct.

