5.3 Randomization and Subject Numbering

Prior to enrollment, subjects will be tracked with their initials and a screening number assigned sequentially starting at "S001". Subjects who meet all inclusion criteria and no exclusion criteria will be enrolled into the study and will be assigned a four-digit subject number. The first two digits will be "A1" and will identify the protocol number. The next two digits identify the subject within the site and will be assigned sequentially, with 01 corresponding to the first subject enrolled, e.g. the first enrolled subject will be A101, the second will be A102, etc.

In total, 12 subjects will be enrolled in the study. Stage 1 will be blinded and randomized and there will be an 8:4 ratio between subjects in the MDMA and placebo conditions. An unblinded Randomization Monitor will generate the randomization list. Subjects will be assigned subject numbers and this number will be used to ensure that confidentiality and HIPAA compliance is maintained throughout the study. Upon enrolling a subject, the PI will be provided with an enrollment code for that subject. Container numbers will be pre-printed on the container labels corresponding to doses for individual experimental sessions. Randomization will be performed at least 24 hours before the experimental session for each subject. The therapists will utilize a web-based randomization program to obtain the container assignment for each experimental session. Blinded personnel will conduct all study evaluations in the randomized portion of the study until the blind is broken for each subject per protocol via the web-based randomization program. Detailed instructions will be provided to the site in a separate document.

If there is an emergency requiring knowledge of subject's condition assignment, the blind may be broken for an individual subject. The PI will be provided with sealed emergency unblinding envelopes corresponding to each enrollment code. These sealed envelopes will be stored in a secure limited access area and should remain sealed if there are no emergency unblinding events during the study.

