6.2 Preparation and Administration

6.2.1 Doses

Doses of MDMA to be used in this study will be 75 mg, 100 mg or 125 mg MDMA. Upon enrollment, the first six subjects (Group 1) will be randomized to receive one dose of either placebo (N=2) or 75 mg MDMA (N=4). In the second experimental session one month later, Group 1 subjects randomized to MDMA will escalate to 100 mg MDMA, unless contraindicated by safety and tolerability concerns. The second six subjects (Group 2) will be randomized to receive one dose of either placebo (N=2) or 100 mg MDMA (N=4). In the second experimental session one month later, Group 2 subjects randomized to MDMA will escalate to 125 mg MDMA, unless contraindicated by safety and tolerability concerns. Subjects randomized to placebo in Group 1 and Group 2 will receive placebo in both experimental sessions also scheduled one month apart. The blind will be maintained through the six-month follow-up for each individual subject, after which the blind will be broken. Placebo subjects will be offered an open-label extension (Stage 2) with two experimental sessions scheduled one month apart, in addition to three hour-long integrative sessions during the month after each experimental session. Stage 2 subjects will receive 75 mg MDMA in the first experimental session and will escalate to 125mg MDMA in the second experimental session, unless contraindicated by safety and tolerability concerns from other subjects in Stage 1.

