19.0 Publication Policy

The sponsor recognizes the importance of communicating medical study data and therefore encourages publications in reputable scientific journals and presentations at seminars or conferences. It is understood by the PI that the information generated in this study will be used by the sponsor in connection with the development of the investigational product and therefore may be disclosed to government agencies in various countries. To allow for the use of information derived from the study, it is understood that the PI is obliged to provide the sponsor with complete test results, all study data, and access to all study records. It is mandatory that all data analysis is done on the official monitored sponsor database and that the analysis plan is agreed upon with the sponsor statistician.

Any results of medical investigations with the sponsor products and/or publications/lectures/manuscripts based thereon, shall be exchanged and discussed by the PI and the sponsor clinical research representative(s) prior to submission for publication or presentation. Due regard shall be given to the sponsor's legitimate interests, e.g. manuscript authorship, obtaining optimal patient protection, coordinating and maintaining submissions to health authorities, and coordinating with other studies in the same field.

The full details of the processes of producing and reviewing reports, manuscripts, and presentations based on the data from this trial will be described in the Clinical Trial Agreement.

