8.0 Analyses

In general, nominal variables will be described in terms of frequencies and percentages and analyzed using chi square analysis. Ordinal and non-normal continuous variables will be described using sample median and range, and analyzed by non-parametric statistical tests, and approximately normal variables will be described using sample mean and standard deviations and analyzed by parametric statistical tests. All statistical tests will be two-sided. All p-values will be rounded to and displayed in four decimals. If a p-value less than 0.0001 occurs it will be shown in tables as <0.0001. For any analysis that is called out as parametric, e.g. t-test, the parametric assumptions will be examined. If necessary, nonparametric analyses will be utilized, e.g. Wilcoxon rank-sum test.

Clinical data will be presented in tabular format. Data not subject to analysis according to this plan will not appear in any tables or graphs, but will be included in the data listings. Analyses will be carried out with SAS Version 9.3 or higher. Selected results may be presented graphically using standard graphical software.

Post-hoc exploratory analyses not identified in this SAP may be performed to further examine the study data. These analyses will be clearly identified as such in the final clinical study report.

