8.10.1 Primary Efficacy Analyses

Liebowitz Social Anxiety Scale (LSAS)

The primary efficacy evaluation is the change from baseline to the primary outcome timepoint (visit 13, one month post experimental session 2) in the LSAS score of Social Anxiety (difference score). The primary efficacy comparison on difference scores will be made with independent sample t-tests at an alpha level of 0.05. If the primary hypothesis rejects, pairwise comparisons among the treatment groups will be made with t-tests. If the parametric assumptions for the t-test analyses are not met, the analogous nonparametric methods will be used (Wilcoxon Rank Sum Test). If data has normal distribution, Cohen's d placebo-subtracted effect size will be estimated on mean difference scores from baseline to Visit 13 with confidence intervals.

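### Protocol 12.0 counts two sessions per subject as independent observations (16 vs 8), although 8 vs 4 subjects are randomised and the SAP uses one value per subject

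*Protocol*

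**What the plan says.** Protocol 12.0 describes the principal effect-size estimates from blinded data. All Stage 1 MDMA sessions, n=16, are "to be compared with all data from placebo sessions (n=8), with each experimental session treated as an independent observation". The same paragraph sets p at 0.05 and lists eight scales: BDI-II, STAI, PSS, IRI, RSES, ERQ, TAS-20 and QoL-Q. It ends: "Effect size will be used to determine the appropriate sample size for future studies". It names no test and promises no interval. The LSAS, which is the primary outcome, is not in the list, but an earlier sentence of 12.0 is general: "Effect size for all outcome measures will be estimated".

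Randomisation is by subject. Protocol 5.3 says that "there will be an 8:4 ratio between subjects in the MDMA and placebo conditions", and Protocol 6.2.1 says: "Subjects randomized to placebo in Group 1 and Group 2 will receive placebo in both experimental sessions also scheduled one month apart". MDMA subjects likewise stay in their arm, at an escalated dose.

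The SAP uses a different unit. Section 8.10.1 takes the change in LSAS from baseline to visit 13 (V13), one value per subject: "The primary efficacy comparison on difference scores will be made with independent sample t-tests at an alpha level of 0.05". Section 8.10.2 applies the same method to the secondary measures. The SAP contains no session-level test and does not say that it replaces the protocol rule.

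**The concern.** Two scores from one person are usually positively correlated. Counting them as separate people credits the comparison with more information than 12 subjects supply. The p-value then tends to be too small, and any standard error or interval attached to d too narrow. A nominally significant result could come from the counting rule alone.

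The two documents also give different answers to a basic question: is the comparison 16 vs 8 or 8 vs 4? A reader of the protocol would take the session-level result as the principal estimate. A reader of the SAP would not expect to see it at all.

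**Working it through.** **Inputs.** Subjects: 8 and 4 (Protocol 5.3). Blinded sessions per subject: 2 (Protocol 2.3, 5.2.3). Threshold: 0.05 (Protocol 12.0). Two-sided testing and the t-test come from SAP 8.0 and 8.10.1, because Protocol 12.0 names no test; a pooled-variance t-test is assumed. The correlation rho between a subject's two values is not in the documents, so a range is shown. Protocol 5.1.2 quotes test-retest values of 0.62 to 0.71 for the IRI. These describe raw scores and are indicative only.

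**The plan's own count.** 8 × 2 = 16 and 4 × 2 = 8. It reproduces exactly as subjects times sessions.

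**Which scales can reach 16 vs 8.** In Protocol Table 2, BDI-II, STAI, PSS, IRI and RSES are taken after each session. The LSAS is too, if the general sentence in 12.0 brings it under the rule. ERQ and TAS-20 appear only at V5, V13 and V14, and QoL-Q only at V5 and V14, so 16 vs 8 cannot be formed for these three from that table. Protocol 3.2 does ask for ERQ and TAS-20 one month after each session, and 5.2.6 is ambiguous on them. The TASIT is not in the list and has its own paragraph in 12.0, so it is left aside.

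**Information.** With two values per subject, the effective numbers are 16/(1+rho) and 8/(1+rho). At rho 0.5 this is 16/1.5 = 10.7 and 8/1.5 = 5.3.

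**True error.** At least 200,000 trials were simulated per setting: 8 and 4 subjects, two equally correlated normal values each, single-session SD of 1, and no treatment difference. The pooled t-test on 16 vs 8 (22 df) was compared with a t-test on subject means, 8 vs 4 (10 df). The subject-level test stayed at about 5% throughout. Session means may differ, for example because doses escalate, so a shift between sessions in both arms was also tried; its sizes are assumptions.

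**p for an observed session-level d of 1.0.** On 16 vs 8, t = 1/√(1/16+1/8) = 2.309 on 22 df, p = 0.031. For subject averages, allow for the fact that the pooled session variance is on average below 1. The within-arm sums of squares have expectation 24 − 2(1+rho), and dividing by 22 gives 1 − rho/11. With equal session means, typically,

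t = √(1−rho/11) / [√((1+rho)/2) × √(1/8+1/4)] on 10 df.

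At rho 0.5: 0.977/(0.866 × 0.612) = 1.842, p = 0.095. The smallest significant session-level d is 2.074 × 0.433 = 0.90 on 16 vs 8. On averages it is 2.228 divided by the t above, for example 2.228/1.842 = 1.21.

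| rho | True error, equal session means | 0.5 SD shift | 1 SD shift | p on averages (d = 1.0) | Smallest significant d |
|---|---|---|---|---|---|
| 0 | 5.0% | 4.4% | 2.8% | 0.044 | 0.96 |
| 0.2 | 7.5% | 6.5% | 4.4% | 0.063 | 1.07 |
| 0.5 | 11.6% | 10.3% | 7.4% | 0.095 | 1.21 |
| 0.7 | 14.5% | 13.0% | 9.5% | 0.117 | 1.30 |
| 0.9 | 17.6% | 15.8% | 11.7% | 0.139 | 1.39 |

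At rho 0 the sessions really are independent, yet p still moves from 0.031 to 0.044. That step is loss of degrees of freedom and not over-counting.

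**Effect on d itself.** With a true d of 0.8 and equal session means, the mean estimate is 0.83 to 0.89 on 16 vs 8, against 0.87 with one value per subject. The excess over 0.8 in the latter is the usual small-sample bias: 0.8/(1 − 3/39) = 0.87. Under a 1 SD session shift, the session-level mean falls to about 0.73 to 0.76, because the shift enters the pooled SD.

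**The case against.** The strongest reply is that the SAP has already dealt with this. It gives a named test on one value per subject for the LSAS and the secondary measures. SAP 8.0 adds: "Data not subject to analysis according to this plan will not appear in any tables or graphs". Sections 8.0, 8.10.3 and 8.11 leave room for a session-level test only as labelled post-hoc work, and Protocol 19.0 requires that "the analysis plan is agreed upon with the sponsor statistician". This confines the practical harm. It does not withdraw the protocol sentence, which still defines the principal estimate on another unit.

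A second reply is that little depends on the p-value. Protocol 12.0 calls the trial primarily a safety study, SAP 2.0 calls it exploratory with no multiplicity correction, and Protocol 12.1 expects low power for small or moderate effects. Later studies are sized from d. This also stands, and it limits the weight of the point. It does not make the counting right.

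A third reply is that a change between sessions widens the pooled SD and offsets the inflation. That is true in part. At a 1 SD shift and rho 0.2 the error is 4.4%, below nominal, but at rho 0.5 and above it remains 7.4% or more.

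**Conclusion.** The rule in Protocol 12.0 is wrong as written, and the two documents conflict on the unit of analysis. If it were applied with a two-sided pooled t-test, the true error of a nominal 5% test would be about 7.5% to 17.6% for rho between 0.2 and 0.9 with equal session means, and about 4.4% to 11.7% with a 1 SD shift in both arms. The figures rest on an assumed rho, an assumed test and normal data.

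A reader might infer more than this, and four stronger readings are not supported:

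- **That the SAP's efficacy tests are inflated.** They use one change per subject, and that unit is sound.
- **That every listed scale is affected.** On Table 2, three of the eight cannot supply a value after each session, and whether the LSAS is covered is unclear.
- **That inflation is certain.** It depends on rho and on the shift between sessions.
- **That future sample sizes would rest on an exaggerated d.** With equal session means d changes little, and under a large session shift it falls.

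The point merits correction before analysis, but its consequence is limited.

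**What to change.** In Protocol 12.0, delete the n=16 and n=8 basis and the clause that declares sessions independent. State instead that between-arm effect sizes and p-values use one value per subject, 8 vs 4. They should follow the SAP's baseline-to-V13 analysis for the LSAS and for every measure scheduled at V13. QoL-Q needs an exception: Table 2 does not schedule it at V13, so its comparison should use the 6-month visit (V14), and SAP 8.10.2 should say the same.

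If the sponsor wants to use both sessions, fit a mixed model with a random subject effect, session as a fixed effect and small-sample degrees of freedom. Standardise d by a single-session SD. With a true d of 0.8 and rho 0.5, dividing by the SD of subject means gives 1.00 on average, against 0.87 for one value per subject.

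The change is one of wording and needs no new data or subjects. The cost is that the reported uncertainty becomes wider.

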5.4 Removal of Subjects from the Study

Subjects can withdraw consent at any time without prejudice. The therapists can withdraw a subject if, in their clinical judgment, it is in the best interest of the subject or if the subject cannot comply with elements of the protocol that are critical for safety or for the scientific integrity of the study. If the therapists withdraw a subject from the study, the therapists will explain the reason for withdrawing the subject. The reason for early termination will be recorded in the subject's Source Records and CRF.

If a subject develops any exclusion criteria that in the opinion of the Medical Monitor, affects the safety of the subject, including psychiatric diagnosis, pregnancy, or requiring use of excluded medications, the subject will discontinue treatment but remain in the study for follow-up purposes. Whenever possible, the tests and evaluations listed for the follow-up will be carried out. Efforts will be made to obtain information about AE outcomes, if deemed necessary by the PI, Data Safety Monitor, Medical Monitor, and/or sponsor.

Subjects discontinuing treatment before the first experimental session will be replaced until blinded data has been collected from 12 subjects. Subjects who discontinue participation after the first experimental session will not be replaced, and an intent-to-treat analysis will be conducted with all available data. Subjects discontinuing treatment prior to the second experimental session will be asked to complete integrative therapy sessions, outcome assessments prior to discontinuation and complete the six-month follow-up assessment if possible. The blind will not be broken for these subjects until after the six-month follow-up assessments have been completed.

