8.2 Handling of Dropouts, Missing Data

Early termination visit data for ITT and Safety variables will be analyzed at the closest scheduled visit. If the closest visit has valid data, the early termination data will be assigned to the next available visit.

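### Protocol 12.0 fills missing secondary-questionnaire responses with an undefined sample average, which shrinks or inflates the secondary effect sizes depending on how it is read, and the SAP neither adopts nor withdraws the rule

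*Protocol*

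**What the plan says.** Protocol 12.0 builds averages before it estimates effect sizes. For the periods after each session: "Scores for BDI-II, STAI, PSS, IRI and RSES completed after each of the experimental session will be averaged to produce mean scores for these periods." For the follow-up period it also averages "BDI-II, STAI and PSS scores gathered via postal mail at monthly intervals from two to five months after the second experimental session." Gaps are then handled in one sentence, and the next gives the use: "Missing responses will be replaced with the sample average. These averages will be used for estimates of effect size." The same section sets these estimates "with p value set at 0.05" and says effect sizes will be used to size later trials.

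The protocol does not say whether the sample is all 12 subjects or the subject's arm, or whether a response is an item, a form or a visit score. It gives no variance correction and no sensitivity analysis.

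SAP 8.2, the section on dropouts and missing data, deals only with where early-termination data go: "Early termination visit data for ITT and Safety variables will be analyzed at the closest scheduled visit." It does not mention mean fill. SAP 8.10.2 tests the secondary scales on change from baseline to visit 13, and SAP 8.10.2.1 tests change from visit 13 to the 6-month visit. Neither refers to period averages.

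**The concern.** Single mean fill treats an invented value as an observed one. With 8 and 4 subjects per arm, one unreturned form is 12.5% of the MDMA arm or 25% of the placebo arm. Gaps are plausible, because BDI-II, STAI and PSS go by mail at months 2 to 5 and subjects who stop after session 1 are not replaced (Protocol 5.4).

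The two readings of the rule push d in opposite directions. Because the wording allows both, the choice could be made after the data are seen. At stake are the protocol's secondary effect sizes, which are meant for planning. Required sample size varies as 1/d², so a d of 0.89 in place of 1.03 asks for (1.03/0.89)² = 1.34 times as many subjects, and a d of 1.23 asks for (1.03/1.23)² = 0.70 times as many.

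**Working it through.** The documents give no missing rate, assumed effect, SD or power, so there is no stated figure to reproduce.

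**Inputs.** Allocation is 8 MDMA and 4 placebo (Protocol 5.3). Alpha is 0.05 (Protocol 12.0), two-sided (SAP 8.0). Assumed: normal scores with SD 1, true difference 1 (0 for type I error), values missing completely at random, pooled-SD Cohen's d, pooled-variance t-test.

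**Whole-sample fill.** Let m₁ of 8 and m₂ of 4 whole scores be missing, leaving a = 8 − m₁ and b = 4 − m₂. Each filled value equals the mean of the a + b observed scores, so the expected difference is multiplied by

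1 − (m₁/8)·b/(a+b) − (m₂/4)·a/(a+b).

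- 1 MDMA missing: 1 − 0.125 × 4/11 = 0.95
- 1 placebo missing: 1 − 0.25 × 8/11 = 0.82
- 2 MDMA and 1 placebo missing: 1 − 0.25 × 3/9 − 0.25 × 6/9 = 0.75
- 4 MDMA and 2 placebo missing: 1 − 0.5 × 2/6 − 0.5 × 4/6 = 0.50

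**Arm fill.** The difference is unchanged. Filled values add nothing to the sum of squares, but the analysis counts 10 degrees of freedom instead of ν = a + b − 2. So d is multiplied by √(10/ν), and t is multiplied by

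k = √[(1/a + 1/b) / ((ν/10)(1/8 + 1/4))].

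The true false-positive rate is P(|t_ν| > 2.228/k). For 2 MDMA and 1 placebo missing: ν = 7, k = √[0.5/(0.7 × 0.375)] = 1.380, and P(|t₇| > 1.614) = 15%. The d multiplier is √(10/7) = 1.195, and 1.03 × 1.195 ≈ 1.23.

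**Whole scores missing.** Type I error and median d under whole-sample fill come from simulation. The arm-fill rates come from the formula, and simulation agrees to within half a percentage point.

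| Missing (MDMA + placebo) | Whole-sample: difference | Whole-sample: median d | Whole-sample: type I error | Arm fill: type I error |
|---|---|---|---|---|
| 1 + 0 | 0.95 | 1.03 | 5.6% | 6.9% |
| 0 + 1 | 0.82 | 0.87 | 3.5% | 8.8% |
| 2 + 1 | 0.75 | 0.89 | 5.2% | 15% |
| 4 + 2 | 0.50 | 0.77 | 4.8% | 38% |

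For the 2 + 1 case, analysis of the observed scores alone gives a difference of 1.00, median d 1.03 and type I error 5.1%.

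**One visit missing inside a three-visit average.** This fits BDI-II and STAI after each session (visits 7 to 9 and 11 to 13 in Protocol Table 2). Only one of three visits is affected, so the loss is divided by three:

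- one placebo visit: 1 − 0.182/3 = 0.94
- one MDMA visit: 1 − 0.045/3 = 0.985, about 0.99
- one visit each in 2 MDMA and 1 placebo subjects, at different visits: 1 − (2 × 0.045 + 0.182)/3 = 0.91

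Simulated with an assumed between-visit correlation of 0.6, the arm-fill false-positive rate in these cases is about 6 to 8%. In the last case, whole-sample fill gives median d 1.17, against 1.18 when each subject's own available scores are averaged.

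Whole-score loss is the relevant model for PSS, IRI and RSES after session 1, where Table 2 schedules a single form (visit 7).

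**The case against.** The strongest reply is that the SAP has moved on. Its secondary tests use visit-13 change and visit 13 to 6 months, it computes no period average, and the mailed rounds enter no specified SAP test. That stands as a limit on reach: the exposure is Protocol 12.0's own effect sizes. It does not dispose of the point, because the SAP never says that the protocol's averages and fill are dropped.

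Second, the scales are secondary, the study is declared exploratory, and d is imprecise here. Near d = 1 its standard error is about √(12/32 + 1/24) = 0.65, so a shift from 1.03 to 0.89 is about a fifth of one standard error. That is a fair argument against the top severity. It does not justify keeping a rule that biases the estimate and is nearly free to remove.

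Four stronger readings are tempting, and the documents do not support them:

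- **The primary result is compromised.** The fill rule does not name the LSAS, and SAP 8.10.1 states no fill.
- **Either reading always gives a wrong d and a wrong p-value.** Whole-sample fill keeps type I error at or below about 5.6% in the cases checked. With one MDMA score missing, median d is 1.03 with or without the fill. The false-positive inflation belongs to the arm reading, which is the less natural one.
- **Every gap costs as much as a lost whole score.** Within a three-visit average the effect is far smaller. If a response means a single item, it would be smaller again; item-level fill was not simulated.
- **Protocol 5.4 contradicts the rule.** Its wording, "an intent-to-treat analysis will be conducted with all available data," follows from not replacing subjects who stop after session 1. It mainly settles who is analysed and does not forbid filling a gap in a scale average. The tension is weak at most.

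**Conclusion.** The rule is wrong as written and should be fixed; it is not a must-fix.

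The direction is certain once a reading is chosen. Whole-sample fill shrinks the difference. Arm fill inflates d and false positives.

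The size depends on a missing rate that the documents do not give. It runs from negligible (one MDMA visit out of three) to material (whole scores missing in a quarter of each arm: a 25% loss of the difference under one reading, or three times the nominal error rate under the other).

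These figures assume normal data missing completely at random and one value per subject or period. Missingness related to outcome would add bias that is not modelled here. Protocol 12.0 also treats sessions as independent observations; that is a separate matter and is not counted here.

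**What to change.** In Protocol 12.0, delete the mean-fill sentence. Form each subject's period average from that subject's own available scores, and leave a subject with no score in the period as missing. Report the number observed per arm beside each d and its confidence interval.

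In SAP 8.2, state that the protocol's mean fill is withdrawn and that no mean fill applies to the visit-13 and 6-month comparisons.

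The cost is a sentence or two in each document and a slightly smaller n for some secondary scales. No new data and no change to study conduct are needed.
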